TGW are at dramatically elevated risk of HIV, substance use, and psychiatric problems. Structural disadvantages in employment and housing set the stage for a range of health problems. There have been no probability studies examining HIV prevalence in TGW, despite evidence that TGW are at very high risk for HIV. A recent meta-analysis using testing data from convenience samples estimated the HIV prevalence among TGW in the US at 21.7% (95% CI: 18.4%-25.1%).⁶ A second meta-analysis examining HIV prevalence in TGW in the US found that, in studies conducting HIV testing, 27.7% (95% C.I.: 24.8%-30.6%) tested positive.⁷ This meta-analysis also reported that HIV rates were consistently highest in African American TGW (56.3%; 95% C.I.: 50.1%-62.4%), relative to other racial groups. Overall, TGW are 34.2 times more likely to be living with HIV than the general US adult population.⁶ TGW also have high rates of undetected HIV infection.²² Research with TGW shows high rates of sexual risk behavior, including unprotected sex and sex with multiple partners.^{7,23-25} Prior work has identified transactional sex, including formal commercial sex work (CSW) as a crucial risk factor for HIV infection in TGW.²⁶⁻²⁸ Rates of transactional sex among TGW are high, with estimates ranging from 15% to 42%.^{1,2,7} Transactional sex is especially common in TGW living in poverty.²

Substance use. TGW also report high rates of substance use,²⁹⁻³³ with a mean of 26.7% (95% CI: 24.5-29.0%) reporting the use of illicit drugs other than marijuana.⁷ Additional research has documented injection risk behaviors in TGW.³⁴ In most groups, injection risk is due to the use of illicit drugs. Among TGW, some individuals also inject hormones or inject silicone directly into the body in an effort to feminize body shape and features.³⁵ Sharing needles during this process may be an additional HIV risk behavior for some TGW.

Psychiatric problems. Research has consistently shown that TGW are disproportionately burdened by psychiatric problems^{8,12,31,36-37} For example, in a recent case-control study of over 5,000 transgender veterans and 15,000 non-transgender veteran controls, transgender veterans had higher rates of psychiatric diagnoses in each of the 10 diagnostic categories examined, including depression, PTSD, panic disorder, and alcohol abuse.⁸ Suicide attempt rates may be 8-10 times higher among TGW as the general population.^{1-2, 37-39}

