Aim 2: Develop an integrated microeconomic intervention for HIV prevention tailored for economically disadvantaged TGW which addresses multiple economic vulnerabilities in two U.S., HIV-prevalent, and resource-poor metropolitan areas. We will work with TGW in the Richmond, VA and St. Louis, MO metro areas as well as city and community partners (e.g., banks, government agencies, community-based organizations) to develop and test each of the proposed intervention components: supportive economic services, employment readiness training, financial education, gender transition financial supports, and economics-based HIV education targeting uptake of recent biomedical HIV prevention advances (e.g., PrEP). After the delivery of each module, a process measure will be administered that assesses the participants' qualitative and quantitative reactions to the material in that module.

Aim 3: Using a randomized experimental study design, evaluate the feasibility and preliminary efficacy of the integrated microeconomic intervention for economically disadvantaged U.S. TGW in reducing economic vulnerability and HIV sexual risk-taking. We will conduct a small experimental pilot-test of the integrated microeconomic intervention versus control with n = 50 TGW per arm with assessment of objective economic and behavioral indicators of HIV risk at 3, 6, and 9 months. As this is a two-site study, in Richmond this will include a total of 50 TGW with 25 TGW per arm.

4. * Describe the scientific benefit or importance of the knowledge to be gained:

In addition to the direct benefits of participation, this research is expected to yield important new information on developing HIV risk reduction interventions for people at high risk for infection. Thus, we feel that the benefits of participation far outweigh the risks.

The summary of the NIH expert panel that reviewed this work stated:

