Randomization. Fifty participants in each study site will be randomized to the intervention or wait-list minimal treatment control group. Assuming 80% retention, this will yield a total sample size of 80 (40 in each site). When assigning participants to treatment/control, we will use urn randomization, an adaptive randomization procedure that ensures approximately equal group sizes while approaching complete randomization.⁹⁴ Adherence to the intervention and supervision of interventionists. Sessions will be conducted in private spaces at our community partner locations according to the guidelines in the treatment manual developed in Aim 2. Facilitators will follow checklists developed for each session and will complete a post-session quality assurance form after each session. All study sessions will be digitally recorded. Study investigators will listen to the first recording of each session and provide feedback to interventionists regarding adherence and quality of administration. Thereafter, study investigators will listen to 20% of all recordings (chosen randomly) and provide feedback as needed. To ensure consistency across study site, investigators will listen to audiotapes and provide feedback for both study sites. Monthly group supervision with interventionists will be conducted by the investigators.

Tracking and retention procedures: As it is common for economically marginalized individuals to move frequently and to be financially unable to maintain consistent phone service, comprehensive tracking information will be collected and updated monthly. This information will include home addresses and phone numbers, but also email addresses, social media account information (e.g., Facebook, Instagram) and contact information for individuals who would know how to reach the participants (e.g., friends, family, health care providers, emergency shelter staff). Participants will also be asked to update contact information at the end of each intervention/assessment session. To increase session attendance, we will offset transportation costs.

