Mental health. Participants will complete the 18-item version of the Brief Symptom Inventory (BSI-18).¹⁰⁵ The BSI-18 contains well-validated scales assessing symptoms of depression, anxiety, and somatic distress. Norm information is available. This measure was internally consistent in a TGW sample in our prior work.^{25,88}

Data analysis. Due to the pilot and feasibility objectives and the size limitation of this study, emphasis of the comparative analysis of the intervention impact will focus primarily on estimation of potential mean changes associated with the intervention for planning purposes rather than confirmatory hypothesis testing. GEE models and mixed models would be ideal to use for data analysis; however, since we will be recruiting in two cities and analyzing data across four time points with a relatively small sample size (n=50 to yield final samples of 40), we will use less complex analyses for this study. Baseline characteristics of the two groups will be compared (t-tests for continuous variables, chi-square analyses for dichotomous and other categorical variables). Variables that are significantly different between the two groups at baseline will be controlled for if the sample size allows for us to do so. Two sets of primary analyses will be conducted for this small experimental trial. First, changes over time will be compared between the two groups, using repeated measures ANOVA for continuous variables (e.g., income) and McNemar♦s test for dichotomous variables

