(e.g., % engaged in biomedical prevention strategies of ARV use or PrEP). These mixed repeated measures ANOVAs will be conducted between the groups between baseline and each follow-up time point. We hypothesize that the integrated microeconomic intervention group will have reductions in economic and behavioral vulnerability to HIV relative to the wait-list minimal treatment control group. The second primary analysis will involve simple repeated measures ANOVAs for the integrated microeconomic intervention group only. While potential effects of maturation and history weaken our causal conclusions based on this analysis, because of the relatively small sizes of our two groups we feel it will validate our results of the mixed repeated measures ANOVA between the groups. We will use intent-to-treat analyses, using standard assumptions for those in the intervention group lost to follow-up. We will have .88 power to detect a medium effect size ($f^2 = .25$) for repeated measures ANOVA (assuming $r = .5$ for outcomes over time) and .8 power to detect a medium effect size ($f^2 = .15$ or the equivalent of partial $R = .36$) with three predictors for multiple regression. We will also compute effect sizes for use in future power analyses.

During Aim 3, we will also recruit a small number of individuals (10 total across study sites, 5 in Richmond) who report discrimination from religious organizations on the baseline assessment to participate in 60-90 minute qualitative interviews assessing those experiences. These will be digitally recorded and transcribed for qualitative analysis, similar to Aim 1. All protections used in Aim 1 will also be used here. The qualitative interview guide has been uploaded.

8. * The IRB only reviews research procedures, so differentiate which of the study procedures are:

- a. Being performed exclusively for research purposes (i.e. they would not otherwise be done apart from this study).**
- b. Alterations of routine procedures (e.g. the study is altering the timing, frequency, method, location, amount, etc.).**
- c. Being done for other purposes and whose data/results will be used secondarily in the study (e.g. standard medical or psychological tests, routine education practices, quality improvement initiatives, etc.).**

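### HIV status and baseline transactional sex are neither balanced by the urn nor pre-specified as covariates, and the baseline-significance rule would leave most 10-point gaps unadjusted

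*Combined protocol and SAP*

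**What the plan says.** Background, Rationale and Goals, item 3, sets the size of the trial: "We will conduct a small experimental pilot-test of the integrated microeconomic intervention versus control with n = 50 TGW per arm". It adds that "in Richmond this will include a total of 50 TGW with 25 TGW per arm". Study Procedures, item 7, Specific Aim 3, gives the allocation method under Randomization: "we will use urn randomization, an adaptive randomization procedure that ensures approximately equal group sizes while approaching complete randomization". No balancing covariate is named. Fifty women are randomised at each site, so balance within site is implied.

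Under Assessment procedures and measures, the primary behavioural indicators include verified PrEP enrolment for HIV-negative women and a verified ARV prescription for HIV-positive women. They also include transactional sex and counts of commercial sex work (CSW) transactions and partners. HIV testing, unprotected sex and number of partners are listed too, and apply to everyone.

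Under Data analysis, the comparison is of change between baseline and each follow-up, by repeated measures ANOVA for continuous variables and McNemar's test for dichotomous ones. The example of a dichotomous outcome is the percentage "engaged in biomedical prevention strategies of ARV use or PrEP". The rule on imbalance reads: "Variables that are significantly different between the two groups at baseline will be controlled for if the sample size allows".

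**The concern.** These two factors are more than general prognostic variables. HIV status decides whether a woman is scored on PrEP or on ARVs. A woman who reports no transactional sex at baseline cannot reduce it, and Study Population, item 4, makes transactional sex only one of several alternative entry criteria. If either factor splits unevenly, the arms differ in room to change, and comparing changes does not remove that.

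The plan's only safeguard is a baseline significance test. With 50 per arm such a test detects only large gaps, and even a detected gap is adjusted for only if numbers permit. The trial is meant to estimate effect sizes for later power analyses, so one chance-distorted estimate could be carried into the next trial.

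**Working it through.** **The plan's own figure.** The plan gives no figure for imbalance. Its power figure can be checked and confirms the sample size used here. With λ = f²·N·m / (1 + (m − 1)r), f = .25, N = 100, m = 4 and r = .5, λ = .0625 × 100 × 4 / 2.5 = 10. On 1 and 98 df at two-sided α = .05 (assumed; not stated) power is .879, matching the stated .88. This reads the printed f² = .25 as f = .25 and counts all 100 women. With the 80 expected to be retained, λ = 8 and power is .80.

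**Inputs from the background section.** HIV prevalence is put at 21.7% and 27.7% in two meta-analyses, and at 56.3% in African American TGW; the sample is expected to be predominantly African American. On transactional sex: "Rates of transactional sex among TGW are high, with estimates ranging from 15% to 42" per cent.

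**Step 1: chance gaps at 50 per arm.** The SD of the gap is √(2p(1 − p)/50). The probabilities come from two independent binomials, and significance is by uncorrected chi-square at .05.

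| Prevalence | SD (points) | P(gap ≥ 10) | P(gap ≥ 20) | Share of ≥ 10-point gaps not significant |
|---|---|---|---|---|
| 15% (transactional sex, low) | 7.1 | 21% | 0.8% | 73% |
| 21.7% (HIV) | 8.2 | 27% | 2.1% | 81% |
| 27.7% (HIV) | 9.0 | 31% | 3.3% | 84% |
| 42% (transactional sex, high) | 9.9 | 36% | 5.4% | 85% |
| 56.3% (HIV, high) | 9.9 | 36% | 5.5% | 85% |

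Significance needs a gap of about 1.96 × SD, or 14 to 20 points. At 40 per arm the share of 10-point gaps missed is 80% to 87%.

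**Step 2: a simulated urn.** The urn parameters are not given, so I assumed one starting ball per arm and one opposite-arm ball added after each draw. Run by site, a 10-point gap occurs in 16% to 33% of trials per factor, somewhat below Step 1. It occurs on at least one of the two factors in 35% to 53%. Running the urn within site × HIV status × transactional sex cuts the latter to 10% to 21%.

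**Step 3: effect on the planned change comparison.** Take a 10-point gap as +5 points in one arm and −5 in the other.

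*ARV or PrEP.* Assume baseline use of 60–80% (ARV, HIV-positive) and 10–30% (PrEP, HIV-negative), uptake among non-users of 20–30% in the intervention arm and 5–10% in control, and 5% loss among users. The shift is 0.05 × [(u_I + .05) + (u_C + .05)] × (b₊ − b₋), where u is uptake and b baseline use. It runs from 0.05 × .35 × .3 = 0.5 points to 0.05 × .50 × .7 = 1.75 points. Simulation at 40 per arm gave 0.2 to 1.7 points, and almost no precision gain from stratifying by HIV status (SD ratio 0.97 to 1.01).

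*Transactional sex.* Assume stopping rates s of 30–50% in the intervention arm and 10–30% in control, and 5% new starts in each. The shift is 0.05 × (s_I + s_C + 2 × .05). It runs from 0.05 × .50 = 2.5 points to 0.05 × .90 = 4.5 points; without new starts it is 2 to 4. With a 20-point difference in stopping rates, the true effect would be p × 20 points: 3.0 at 15% prevalence and 8.4 at 42%. A baseline term removes the shift and cuts the SD of the estimated difference by about 5% to 15%.

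**The case against.** The strongest reply is that this is ordinary sampling error. Randomisation is unbiased on average, the trial is a pilot aimed mainly at feasibility and estimation, and the planned analysis of change already removes part of any baseline gap. All of that stands. It limits the point to precision and to the reliability of one realised estimate. It does not defend the significance rule, which serves neither purpose.

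A reader might infer four stronger things that the documents do not support:

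- *That sizeable imbalance is likely.* For a single factor, 10 points has a 21% to 36% chance. It passes even odds only for the two factors together, and then only in some scenarios. At 50 per arm, gaps of 20 points or more are rare and would be flagged.
- *That 10 points of HIV imbalance shifts the ARV-or-PrEP result by 3 to 7 points.* That is 10% of a 30- to 70-point difference in use, so it describes follow-up levels. The plan compares change.
- *That only a subset of women is informative for the biomedical outcome.* HIV-positive women contribute through ARVs and HIV-negative women through PrEP.
- *That ARV and PrEP will only be reported pooled.* The pooled percentage appears as an example, and the assessment section defines the two indicators separately by HIV status.

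The prevalence inputs are also uncertain. The 56.3% figure is for African American TGW alone. The sample is selected for economic and behavioural risk, so transactional sex may exceed 42%; uneven splits of those who report it would then matter less.

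**Conclusion.** The concern holds as a moderate, inexpensive improvement. No baseline factor beyond arm size (and, by implication, site) is balanced by design. The adjustment rule would miss 73% to 85% of gaps of 10 points or more at 50 per arm. The consequence is small for ARV or PrEP by HIV status, under 2 points per 10 points of imbalance. It is material for transactional-sex outcomes, at 2.5 to 4.5 points against assumed true effects of 3.0 to 8.4.

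These figures rest on the background prevalences, equal arms, α = .05 and the assumed uptake, stopping and starting rates. A larger difference in change between HIV strata would raise the ARV-or-PrEP figure: a 3-point shift needs a difference of about 30 points. Nothing here suggests systematic bias.

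**What to change.** In Data analysis, delete the significance-gated rule. Pre-specify terms for site, self-reported HIV status and baseline transactional sex (or the outcome's own baseline value) in the between-arm analyses, whatever the baseline p-values. McNemar's test cannot carry covariates, so dichotomous outcomes need a regression or a stratified comparison of arms. Report PrEP among HIV-negative and ARV use among HIV-positive women separately before combining them.

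Optionally, in Randomization, use HIV status and transactional sex as urn balancing factors within site. This works only where those answers are recorded before allocation. The documents do not say that baseline precedes allocation, and consent is taken just before the first session.

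The cost is two or three model degrees of freedom and some misclassification of self-reported HIV status. Crossing all three factors in the urn gives eight cells, some sparse: at the low prevalences, about 50 × .217 × .15 = 1.6 women per site in the smallest, if the factors are independent. No added participants or visits are needed.

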This will include 30 TGW (15 in each site) for qualitative interviews which we believe will be enough to achieve saturation, 20 TGW (10 in each site) for pilot testing of intervention (we believe this will match the size of the intervention group and thus is appropriate for intervention piloting), and 100 TGW (50 in each site) for the randomized controlled trial. The total number above also reflects the numbers we anticipate screening for study inclusion. This will include some individuals who are not eligible and some individuals who are eligible but choose not to participate in study activities other than completing the screening survey. For the RCT the size is justified by power analysis. We will use intent-to-treat analyses, using standard assumptions for those in the intervention group lost to follow-up. We will have .88 power to detect a medium effect size ($f^2=.25$) for repeated measures ANOVA (assuming $r = .5$ for outcomes over time) and .8 power to detect a medium effect size ($f^2 = .15$ or the equivalent of partial $R = .36$) with three predictors for multiple regression.

4. * List the study inclusion criteria:

For screening, inclusion criteria will include that the participant is a transgender woman and is 18-45 years of age.

For TGW, full study participation, inclusion criteria will require both (i) Economic vulnerability (unemployment or underemployment [less than 20 hours/week], low income [less than the Medicaid poverty threshold], housing insecurity in the past year, or food insecurity in the past year), and (ii) Behavioral vulnerability to HIV transmission: unprotected sex in prior 6 months, transactional sex, multiple sexual partners, 1-time sexual partner, sex with a partner of unknown HIV status, sex under the influence of drugs or alcohol. Participants will be recruited if they are age 18 or older. Based on our prior work, we expect participants meeting these guidelines to be relatively young (mean age = 32, SD =10) and predominantly African American. Based on data from our pilot work, we expect around 45% of individuals screened to meet eligibility requirements.

These are the inclusion criteria for TGW for Aims 1, 2, and 3.

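### The .8 power quoted for the RCT belongs to a three-predictor regression found in none of the described analyses, and the dichotomous primary indicators have no power or precision figure

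*Combined protocol and SAP*

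**What the plan says.** Study Population, item 3, plans "and 100 TGW (50 in each site) for the randomized controlled trial" and states that "For the RCT the size is justified by power analysis". Two figures follow. One is .88 for repeated measures ANOVA. The other is .8 for a medium effect, f2 = .15, "or the equivalent of partial $R = .36$) with three predictors for multiple regression". The Data analysis text under Study Procedures, item 7, repeats both and continues: "with three predictors for multiple regression. We will also compute effect sizes for use in future power analyses".

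The same Data analysis text sets out the Aim 3 analyses:
- baseline comparisons by t-test and chi-square;
- a first primary analysis comparing change between arms, by repeated measures ANOVA for continuous variables and McNemar's test for dichotomous ones, with ARV or PrEP use as the dichotomous example;
- a second primary analysis, a repeated measures ANOVA in the intervention arm alone.

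Baseline variables that differ between arms are to be controlled for if the sample size permits. The stated emphasis is on estimating mean changes rather than on confirmatory testing.

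Assessment procedures and measures makes economic and behavioral vulnerability the primary outcomes, each with a list of objective and subjective indicators. Many of these are yes/no. No control rate, detectable difference, power or interval width is given for any of them.

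**The concern.** A power statement that supports a sample size should belong to an analysis the trial will run. Here one of the two figures belongs to a model with no stated outcome, no named predictors and no place in the analysis plan. A reader could take .8 for a medium effect as the trial's sensitivity on outcomes that the ANOVA figure does not cover. Those are the dichotomous indicators, including verified HIV testing, linkage to care, PrEP enrollment and ARV prescription.

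A second gap makes this worse. McNemar's test compares a person's status at two times. It does not compare arms, so the plan as written names no between-arm test for these outcomes to which a power or precision figure could attach.

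**Working it through.** **Inputs.** Aim 3 has "integrated microeconomic intervention versus control with n = 50 TGW per arm". Randomization assumes 80% retention, giving 80 analysed, about 40 per arm. Alpha is not stated; .05 (two-sided for proportions) is assumed throughout.

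**1. The plan's own figure.** f2 = .15 gives R = sqrt(.15/1.15) = .361, which matches the stated .36. For the joint test of three predictors, power comes from the noncentral F with noncentrality f2 × N and 3 and N − 4 degrees of freedom.

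| N | Joint test, 3 predictors | One coefficient in the same model |
|---|---|---|
| 76 | .796 | .915 |
| 77 | .802 | .918 |
| 80 | .819 | .928 |
| 100 | .905 | .970 |

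The .8 fits the joint test at 77 to 80. It does not fit a single-coefficient test, which is what an arm effect would need. So it is the power to show that three predictors together explain R-squared = .15/1.15 = .13.

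**2. How many primary indicators are dichotomous.** Objective: employment, housing stability, HIV testing, linkage to care, PrEP and ARV are yes/no, 6 of 9 (the others are income, savings and pill counts). Subjective: employment status, housing status, transactional sex and substance use with sex, 4 of 12. The total is 10 of 21 (48%), or 11 of 21 (52%) if partner type is scored yes/no. The documents do not classify the indicators, so this count is a reading of the list.

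**3. Between-arm precision at 40 per arm.** Control rates of 10% to 50% are assumed.
- CI half-width, equal proportions: 1.96 × sqrt(2p(1 − p)/n).
- Detectable difference d at 80% power: solve n = [1.96 × sqrt(2m(1 − m)) + 0.842 × sqrt(p1(1 − p1) + p2(1 − p2))]² / d², where m is the mean of p1 and p2.

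| Control rate | Half-width (points) | Detectable difference (points) |
|---|---|---|
| 10% | 13.1 | 26.0 |
| 20% | 17.5 | 29.4 |
| 30% | 20.1 | 30.7 |
| 40% | 21.5 | 30.7 |
| 50% | 21.9 | 29.5 |

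Check at 30% against 60.7%: m = .4535, so 1.96 × .704 + 0.842 × .670 = 1.944; 1.944/.307 = 6.33; 6.33² = 40.

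**4. PrEP and ARV subsets.** PrEP is verified only in HIV-negative and ARV only in HIV-positive participants. The Background gives HIV prevalence of 21.7% and 27.7% from two meta-analyses and 56.3% for African American TGW. The inclusion criteria text expects a predominantly African American sample, so the whole range is relevant.

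| Prevalence | HIV-positive per arm | HIV-negative per arm |
|---|---|---|
| 21.7% | 40 × .217 = 8.7 | 31.3 |
| 27.7% | 11.1 | 28.9 |
| 56.3% | 22.5 | 17.5 |

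That is about 17 to 31 HIV-negative and 9 to 23 HIV-positive per arm. Over the same control rates, the detectable difference is roughly 30 to 46 points for PrEP and 36 to 63 points for ARV. With 9 per arm and a 50% control rate, the formula does not reach 80% power at any difference.

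**5. Transactional sex.** Power to halve the rate at 40 per arm, by exact enumeration of the pooled z-test: about .20 from 15%, .52 from 42%, .80 from 60% and .90 from 70%. The first two rates are the ends of the Background range for TGW generally; the last two are assumptions.

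**The case against.** The strongest reply is that this is a pilot. The documents say that the RCT is mainly for feasibility and parameter estimation, that testing is not confirmatory, and that effect sizes will be computed for later planning. The .88 figure does address a named primary analysis, and the .8 is expressly labelled as regression, so nothing claims that it covers binary outcomes. This stands as a limit on weight. It does not remove the point: item 3 still justifies the size by power, and the estimation emphasis is worded for mean changes, so proportions have neither power nor precision.

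A reader might infer that the regression will certainly never be run. The documents do not go that far. The application says that only some of the science document was pasted in, and the full document is not available here. The conditional baseline adjustment could also be done by regression. But that provision names no model and no three predictors.

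A reader might also infer that the trial has poor power for transactional sex, using the Background's 15% to 42%. Those rates describe TGW generally. Entrants here must be economically and behaviorally vulnerable, with transactional sex as one qualifying behavior, and no trial baseline rate is given. At an assumed 60% or 70%, halving the rate has power of .80 or .90.

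Finally, the 26 to 31 points come from a two-sample comparison, not from McNemar's test. That objection is right, and it is why the comparison must be named before the figures are used.

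**Conclusion.** The point holds as a mismatch between the power statement and the described analyses. There is no arithmetic error: the .8 is correct for its own inputs, but those inputs belong to a joint test of three unnamed predictors and not to the comparison of arms. About half of the primary indicators have no stated sensitivity. For them, 40 per arm gives a CI half-width of about 13 to 22 points and needs about 26 to 31 points for 80% power. The HIV-status subsets need roughly 30 to 46 points (PrEP) and 36 to 63 points (ARV).

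These sizes assume two-sided alpha of .05, control rates of 10% to 50%, the planned 80% retention, an even split of HIV status between arms, and prevalence between 21.7% and 56.3%. They do not show that the sample is too small for a pilot or that the ANOVA figure for continuous outcomes is wrong; neither conclusion follows from this check.

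**What to change.** In Study Population, item 3, and in Data analysis:

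1. Delete the multiple-regression power figure.
2. For dichotomous indicators, name a between-arm comparison of proportions, noting that McNemar's test is paired within person and does not compare arms.
3. Give its precision at 40 per arm: CI half-width of about 13 to 22 points and a detectable difference of about 26 to 31 points, with alpha and the control rates labelled as assumptions.
4. State that PrEP and ARV are analysed in HIV-status subsets of about 17 to 31 and 9 to 23 per arm, with the matching detectable differences.
5. Extend the estimation emphasis to proportions as well as mean changes.
6. Omit power figures for transactional sex, or show them over a range of assumed baseline rates such as 15% to 70%.

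The cost is a short replacement for the power sentence in two places, plus naming the comparison. The stated sensitivity becomes less favourable. The sample size and data collection do not change.
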